### **4.2 Secondary Objectives**

The secondary objectives of this study are:

- To determine the changes in clinical status measures listed through Day 15:
  - Hospitalization status
  - Duration of hospitalization
  - National Early Warning System 2 Score (NEWS2) Score
- To determine survival status through Day 29

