## 5 TRIAL DESIGN

This will be a phase 1a randomized, open label, multi-center study with approximately 24 subjects. All subjects will receive standard of care per institutional guidelines for treatment of patients with SARS-CoV-2 infection. In addition to standard of care, the brequinar group will receive brequinar 100 mg once daily for 5 days.

The Massachusetts General Hospital (MGH) COVID-19 Treatment Guidance is provided in Appendix D Section 15.4. This guidance provides an example of standard of care instructions for treatment of COVID-19. The guidance is provided as informational only, it is not required that this guidance be used for treatment as standards of care may differ between institutions.

Subjects will have a Screening Visit followed as soon as possible with Study Day 1 (Day 1 may take place on the same day if entry criteria data are available). Study procedures are presented in detail in Section 8. Subjects will be followed through Day 15, with mortality assessed via a phone call/other digital media acceptable to institution on Day 29.

If the subject is being discharged prior to Day 7, see Section 8.4.

It is understood that some assessments may not be conducted if the subject is unable to return to the clinic after discharge due to restricted travel. If an assessment is missed due to after hospital discharge, e.g., samples or blood draws, this will not be counted as a protocol deviation. Any of the study visits may be conducted via telephone if the subject has been discharged from the hospital and is not permitted to or is unable to return to the hospital/clinic for these visits.

Information is to be collected using the electronic health record (EHR) whenever possible. It is not required to perform study-specific laboratory assessments, NEWS 2 assessments, etc. separately for study purposes.

PROTOCOL NUMBER: CCB-CRISIS-01  
PROTOCOL VERSION DATE: 01MAY2020

Page 23 of 55

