### **6.2 Secondary Endpoints**

- Rates of/changes to the below clinical status measures through Day 15.
  - Hospitalization status
  - Duration of hospitalization in days
  - NEWS2 Assessments Days 1, 3, 5, 7, and Day 15 for hospitalized subjects.
- Mortality through Day 29

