### **8.3 Study Discontinuation**

Subjects will remain in the study through at least Study Day 15 (or longer if needed to follow up study drug-related adverse events). Mortality is assessed via a phone call or other digital media at Day 29.

After treatment, participants will be monitored through at least Study Day 15 (or longer if needed to follow study drug-related AEs/SAEs). Participants may discontinue from the study by withdrawing consent at any time or for any reason as presented in [Section 9.7](#).

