- Collect hospital status (hospitalized, hospitalized in ICU, discharged).

**Day 29** (8 AM  $\pm$  3 days)

- Determine survival status from EHR if available or contact the subject by phone call/digital media as acceptable to the institution.

If the subject is being discharged before Day 15, follow the procedures outlined in Section 8.4.

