Death due to disease progression should not be reported as an SAE. Report death from disease progression on the appropriate electronic data capture form.

If a death occurs during the SAE reporting period, the cause of death such as pneumonia, ARDS, or respiratory failure, is considered as the AE and the death is considered its outcome. Death should be considered an outcome, not an event. The event or condition leading to death should be recorded and reported as a single medical concept on the AE eCRF. Generally, only one such event should be reported. "Fatal" will be recorded as the outcome of this respective event; death due to an outcome of an AE will not be recorded as separate event. If the primary cause of death is disease

PROTOCOL NUMBER: CCB-CRISIS-01  
PROTOCOL VERSION DATE: 01MAY2020

Page 37 of 55

progression, the cause of death should be clearly identified as progression of the disease under study.

In cases of surgical or diagnostic procedures, the condition leading to the procedure is considered as the AE instead of the procedure itself. Each AE will be coded by the Sponsor from the verbatim text to a preferred term using a thesaurus based on the Medical Dictionary for Regulatory Activities (MedDRA). For example, record appendicitis, not appendectomy.

The following guidelines will be followed for the recording and reporting of adverse and serious adverse events.

1. The medical history section of the case report form will serve as the source document for baseline events.
  - a. Baseline events are any medical condition, symptom, or clinically significant lab abnormality present before the informed consent is signed.
    - i. If exact start date is unknown, month and year or year may be used as the start date of the baseline event.
2. Adverse events occurring after signing consent are to be recorded in the eCRF using the AE form.
3. Serious adverse events will be reported to the local IRB according to institutional policy.

The descriptions and grading scales found in the revised National Cancer Institute (NCI) Common Terminology *Criteria for Adverse Events (CTCAE) version 4.03* will be utilized for adverse event reporting. (<http://ctep.cancer.gov/reporting/ctc.html>).

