Subjects who are discharged from the hospital before Day 7 will have follow up contacts with study staff (phone calls or other digital media) on Days 7, 15 and 29. Early discharge subjects in the brequinar treatment group will also have samples for safety labs (hematology and chemistry) obtained either at the research facility or at an outpatient laboratory on Study Days  $7 \pm 2$  and  $15 \pm 2$ . The safety laboratory results are to be initially assessed in real time by the Principal Investigator or designated person and the Medical Monitor. Any study drug-related clinically significant out-of-range laboratories or study drug-related adverse events will be followed as needed until resolution or stable.

The in-hospital assessments and phone call visits will specifically ask about possible hematologic toxicity including any evidence of the list below. Early discharge subjects will be provided with a list of the following events in lay terms and will be instructed to call the research team if any of these events occur.

- Ecchymosis/purpura/petechiae
- Epistaxis
- Hemoptysis
- Hematuria
- Gingival bleeding
- Prolonged bleeding time from needle sticks, abrasions or lacerations
- Hematemesis
- Rectal bleeding
- Blood in stool

PROTOCOL NUMBER: CCB-CRISIS-01  
PROTOCOL VERSION DATE: 01MAY2020

Page 42 of 55

- Any other unusual bleeding noted by the subject or caregiver

Any of these symptoms considered clinically significant will be recorded as an adverse event and must be followed until resolved or stable.

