## 15 APPENDICES

### 15.1 Appendix A: CCB-CRISIS-01 Schedule of Events

CCB-CRISIS-01 Schedule of Events	Screen	D1	D2 - D7 (± 8 hours)	Final Visit D15 (± 2 days)	F/U Phone Call 2 weeks/ Survival (± 3 days)
Procedures					
Informed Consent	X				
AE/Concomitant Medications	X	X	D7	X	
Medical history / History of current illness	X				
Demographics, collect Height and weight	X				
Check for Physical Exam abnormalities	X				
Pregnancy Test (urine or serum)	X				
Hematology/Chemistry	X	X (pre-dose)	D7	X	
Inflammatory Markers*		X (pre-dose)	D3, D5, D7	X	
DHO/brequinar PK Sample Collection & Processing		X (pre-dose)	D3, D5, D7	X (DHO only)	
Swab collection for nasopharyngeal viral load		X (pre-dose)	D3, D5, D7	X	
Clinical SARS-CoV-2 testing RT-PCR	X				
Hospital Status			D3, D5, D7	X	
NEWS2 Assessments		X	D3, D5, D7	X	
Dispense Study Medication if assigned to brequinar		X	D2 – 5		
Drug Accountability			D7		
Survival Assessment Day 29					X

Collect information from available electronic health record (EHR), Progress Notes, and medication records; a special visit by research staff is not to be performed. Hematology, Results for Chemistry and available inflammatory markers analyzed locally are to be obtained from the EHR; do not draw another set of labs. Missed samples due to hospital staff too busy or for technical reasons unable to obtain samples will not be counted as protocol deviations.

Note that any visits other than Screening/Day 1 may be conducted via telephone or digital media. Missed samples/assessments when phone visits occur will not be counted as protocol deviations.

\*Inflammatory markers are to be collected from the EHR when available; otherwise process and ship samples to the central laboratory per the Laboratory Manual. DHO and brequinar samples will also be sent to the central laboratory.

Note that if the subject is discharged before Day 15, ensure safety laboratory samples for hematology and chemistry are obtained prior to discharge and on an outpatient basis per Section 8.4.

PROTOCOL NUMBER: CCB-CRISIS-01  
PROTOCOL VERSION DATE: 01MAY2020

Page 53 of 55

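### Mortality through Day 29 rests on one survival check that may be made as early as Day 26, and on health-record evidence that need not reach Day 29, so deaths by Day 29 can be missed

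*Protocol*

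**What the plan says.** All references are to the protocol version of 01MAY2020.

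- **Endpoint.** Section 6.2 lists "Mortality through Day 29". Section 4.2 gives the matching objective: "To determine survival status through Day 29".
- **Timing of the check.** The synopsis and Section 9.5 both place the Day 29 check at ± 3 days. The Schedule of Events in Appendix A heads the column "F/U Phone Call 2 weeks/ Survival (± 3 days".
- **Source of the status, Section 9.5.** "Determine survival status from EHR if available or contact the subject by phone call/digital media as acceptable to the institution". The synopsis has an equivalent instruction.
- **Source of the status, elsewhere.** Section 8.3: "Mortality is assessed via a phone call or other digital media at Day 29". Section 5: "with mortality assessed via a phone call/other digital media acceptable to institution on Day 29". Neither mentions the health record. Section 10.6 says that subjects discharged before Day 7 "will have follow up contacts with study staff (phone calls or other digital media) on Days 7, 15 and 29".
- **Compliance.** Section 9.6 says that procedures done within the stated windows need no deviation report.
- **Recording of deaths.** Section 10 says: "Report death from disease progression on the appropriate electronic data capture form". It does not say which dates that form captures.

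**The concern.** An endpoint with a cut-off at Day 29 needs to know each subject's status up to Day 29. The collection rule does not guarantee this, for two reasons.

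First, the window is two-sided. A contact on Day 26 that finds the subject alive is fully compliant, and nothing calls for a second look. If the subject dies on Day 27, 28 or 29, the recorded status stays alive. This is a gap in collection: no rule in a statistical analysis plan can recover a status that was never obtained.

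Second, where the status is taken from the electronic health record, nothing says how recent the evidence must be. The ± 3 days date the look-up, not the entry that is found. A hospital record with no entry after discharge is silent about a death elsewhere, and that silence could be read as survival.

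Mortality is the hardest clinical outcome in the trial. With about 8 and 16 subjects per arm, a single misclassified death is visible in the reported percentage.

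**Working it through.** **1. Window.** 29 − 3 = 26 and 29 + 3 = 32. The check may fall on any of 7 days, three of them (26, 27, 28) before the cut-off.

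**2. Inputs.** N = 24, split about 8 and 16 (synopsis, Sample Size; Section 7.1). The protocol gives no mortality rate for this population and no sample size calculation (Section 11.5), so there is no stated figure to reproduce. Assumed here: mortality m by Day 29 of 10% or 20%, with a constant hazard from Day 1 to Day 29.

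**3. Formulas.** h = −ln(1 − m)/28 and S(d) = exp[−h(d − 1)], so S(29) = 1 − m. If everyone is checked on day d before Day 29, the expected number of missed deaths is N × [S(d) − S(29)].

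**4. All checks on Day 26 (worst case for the window).**

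| m | Expected deaths by Day 29 | S(26) | S(29) | Missed deaths, N = 24 | Chance of at least one |
|---|---|---|---|---|---|
| 10% | 2.4 | 0.9102 | 0.9000 | 24 × 0.0102 = 0.25 | 22% |
| 20% | 4.8 | 0.8194 | 0.8000 | 24 × 0.0194 = 0.47 | 37% |

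The last two columns use unrounded differences. The chance of at least one is 1 − [1 − (S(26) − S(29))]^24.

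**5. Checks spread evenly over Days 26 to 32.** Only Days 26, 27 and 28 can miss a death, and each has weight 1/7.

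- m = 10%: expected misses if all checks were on that day are 0.245, 0.163 and 0.081. Their sum divided by 7 is 0.07, or 2.9% of the 2.4 expected deaths.
- m = 20%: 0.465, 0.309 and 0.154. Their sum divided by 7 is 0.13, or 2.8% of the 4.8 expected deaths.

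**6. Weight of one death.** 1/8 = 12.5 percentage points in the standard-of-care arm; 1/16 = 6.25 points in the brequinar arm.

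**7. Source of the status, side by side.**

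| Place | Source |
|---|---|
| Synopsis and Section 9.5 | Health record if available, otherwise contact |
| Sections 5 and 8.3 | Phone or other digital contact |
| Appendix A column heading | Follow-up phone call |
| Section 10.6 | Contact by study staff, for discharge before Day 7 |
| Inclusion criterion 3 | Willingness for a Day 29 contact if discharged before Day 15 |

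Two sites, one following Section 9.5 and the other Section 5, would establish the same endpoint in different ways. The number of deaths lost through the health-record route cannot be computed, because the documents give no rate of deaths outside hospital after discharge.

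**The case against.** The strongest reply is that little hangs on this. Mortality is a secondary endpoint, the primary endpoint is safety, all analyses are descriptive, and Section 9.6 asks sites to keep as close to the schedule as they can. Few checks should fall on Day 26, and the evenly spread case costs about a tenth of a death in the whole trial. A hazard that falls over time would reduce it further. All of this stands, and it limits the size of the point.

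On the health record, the natural reading is that it serves only if it shows the status at about Day 29, with contact as the fallback. Section 10.6, inclusion criterion 3 and the Appendix A heading all point to direct contact for discharged subjects, and Section 8.4 says the Day 29 assessment still takes place after late discharge. This also largely stands. A reader might infer that a subject discharged on Day 8 who dies at home on Day 20 would be counted alive by rule. The documents do not prescribe that. It is one possible outcome of passages that disagree.

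A reader might also infer that deaths on Days 30 to 32 would be counted. That does not follow. The endpoint ends at Day 29 by its own words, adverse events are recorded with dates and outcome, and progression deaths have their own form. A late death is excluded once its date is known, and the case report form or the analysis plan, neither shown, may well supply that step.

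None of this removes the early half of the window. A compliant check on Days 26 to 28 leaves the remaining days unobserved.

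**Conclusion.** The point holds in a limited form. As written on 01MAY2020, deaths by Day 29 can be missed because a valid check may precede Day 29, and because the health-record option sets no requirement on how recent the evidence is and conflicts with Sections 5 and 8.3. The documents do not support the claim that deaths after Day 29 are counted.

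The window effect is small: a fraction of one death in 24 subjects under the assumed constant hazard and 10% to 20% mortality, even in the worst case. The health-record effect comes on top and cannot be sized. The change is still worth making, because a missed status cannot be repaired at analysis and one death is a large step in arms of 8 and 16. Later protocol versions are listed but their text is not shown, so whether the wording is still in force needs the sponsor's confirmation.

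**What to change.** 1. Change the window from ± 3 days to 0/+3 days (Day 29 to Day 32) in the synopsis, Section 9.5 and the Appendix A column.
2. Accept a status of alive from the health record only if it holds an entry dated on or after Day 29. Otherwise make the contact that Sections 5 and 8.3 already describe, and align the wording of all these sections.
3. Record the date of death or the date last known alive, and state that only deaths dated on or before Day 29 count towards the endpoint.

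The cost is a few wording changes and, if the form lacks it, one date field. The one real drawback is that the contact window shrinks from 7 days to 4.

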### 9.5.1 **Unscheduled Visits**

Unscheduled visits and tests to assess AEs/SAEs are permitted as needed providing the AE related to study drug or SAE onset occurs within two (2) weeks after the final study dose.

### 9.6 **Compliance with Study Procedures**

The time at which study procedures are conducted should follow the protocol timelines as closely as possible. However, it is recognized in a clinical setting that protocol-specified timings may not occur exactly as specified in the protocol. Provided that activities are carried out within the identified windows it will not be necessary to file a protocol deviation. It is understood that some scheduled study assessments may not be able to be conducted if the subject is unable to return to the clinic after discharge due to COVID-19 restricted travel; it is also understood that crowded hospital conditions/lack of personnel may make it impossible to carry out all requested study procedures; this will not be counted as a protocol deviation. The Day 7 and 15 visits are to be conducted via telephone if the subject has been discharged from the hospital with lab draws for subjects in the brequinar treatment group as described in Section 8.4.

### 9.7 **Early Withdrawal from the Study**

A subject may withdraw from the study at any time for any reason or for one of the reasons listed below. The Sponsor or Investigator may also terminate a subject's study participation after discussion with the other party if it is believed it would be unsafe for the subject to continue in the study.

PROTOCOL NUMBER: CCB-CRISIS-01  
PROTOCOL VERSION DATE: 01MAY2020

Page 35 of 55

Subjects must be withdrawn from the study if any of the following events occur:

- Significant protocol violation or non-compliance, either on the part of the subject or the investigator or other site personnel;
- Decision of the Investigator or Sponsor that removal is in the subject's best interest;
- Severe unrelated medical illness or complication;
- Safety reasons/ significant adverse event;
- Subject request (withdrawal of consent);
- Sponsor decision.

Collect/conduct all evaluations for subjects who withdraw from the study prior to completing the treatment period unless consent is withdrawn.

### **9.8 Early Termination of the Study**

If the Sponsor or an Investigator believes it would be unsafe to continue the study, or for any reason at the Sponsor's request, the study may be terminated at that site or the entire study terminated after discussion with the other parties.

The Sponsor will provide a written statement to the IRB and the relevant regulatory authority with the reasons for termination of the study. This will be conducted within 15 days of the decision to terminate the study.

If the study is terminated, a close out monitoring visit will be performed and applicable procedures will be carried out to close the trial site(s).

PROTOCOL NUMBER: CCB-CRISIS-01  
PROTOCOL VERSION DATE: 01MAY2020

Page 36 of 55

## 10 ADVERSE EVENT REPORTING

An adverse event is any untoward medical occurrence in a patient or clinical trial subject administered a medicinal product and which does not necessarily have a causal relationship with this treatment. An AE can therefore be any unfavorable and unintended sign (including an abnormal laboratory finding), symptom, or disease temporally associated with the use of the medicinal product, **whether or not considered related to the medicinal product.**

Events that occur prior to informed consent will be entered as medical history; AEs that occur after informed consent will be entered on the AE form.

Subjects will be questioned and observed for evidence of AEs, whether or not judged by the Investigator or designated person to be related to study drug. All AEs will be documented in the subject's medical record and CRF. For any pre-existing condition or abnormal laboratory finding that changes in severity after dosing, this change should be recorded as an AE. New abnormal laboratory findings that are clinically significant are considered AEs.

All adverse events will be collected from the time of informed consent through Day 15. After Day 15, collect/record only Serious Adverse Events (SAEs) or those judged by the Investigator or designated person to be related to study drug. AE details are to be documented including start and stop date and times, whether continuous or intermittent, severity, any intervention utilized to correct the event (e.g., medication, surgery, or other therapy), outcome and the relationship to the study drug.

AEs identified in the protocol as critical to the evaluation of safety must be reported to the Sponsor by the Investigator according to the reporting requirements within the time periods specified in the protocol.

AEs determined by the Investigator to be related to study drug must be followed until resolution or until they are considered stable or for at least 30 days after discontinuation of study drug.

Any serious adverse events (SAEs) experienced after 30 days post the last dose of study drug should only be reported to the sponsor if the investigator suspects a causal relationship to the study drug.

Abnormal laboratory values or test results occurring after study enrollment constitute AEs only if they induce clinical signs or symptoms, are considered clinically significant, or require therapy.

Death due to disease progression should not be reported as an SAE. Report death from disease progression on the appropriate electronic data capture form.

If a death occurs during the SAE reporting period, the cause of death such as pneumonia, ARDS, or respiratory failure, is considered as the AE and the death is considered its outcome. Death should be considered an outcome, not an event. The event or condition leading to death should be recorded and reported as a single medical concept on the AE eCRF. Generally, only one such event should be reported. "Fatal" will be recorded as the outcome of this respective event; death due to an outcome of an AE will not be recorded as separate event. If the primary cause of death is disease

PROTOCOL NUMBER: CCB-CRISIS-01  
PROTOCOL VERSION DATE: 01MAY2020

Page 37 of 55

progression, the cause of death should be clearly identified as progression of the disease under study.

In cases of surgical or diagnostic procedures, the condition leading to the procedure is considered as the AE instead of the procedure itself. Each AE will be coded by the Sponsor from the verbatim text to a preferred term using a thesaurus based on the Medical Dictionary for Regulatory Activities (MedDRA). For example, record appendicitis, not appendectomy.

The following guidelines will be followed for the recording and reporting of adverse and serious adverse events.

1. The medical history section of the case report form will serve as the source document for baseline events.
  - a. Baseline events are any medical condition, symptom, or clinically significant lab abnormality present before the informed consent is signed.
    - i. If exact start date is unknown, month and year or year may be used as the start date of the baseline event.
2. Adverse events occurring after signing consent are to be recorded in the eCRF using the AE form.
3. Serious adverse events will be reported to the local IRB according to institutional policy.

The descriptions and grading scales found in the revised National Cancer Institute (NCI) Common Terminology *Criteria for Adverse Events (CTCAE) version 4.03* will be utilized for adverse event reporting. (<http://ctep.cancer.gov/reporting/ctc.html>).

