--	--

	
they have assessments through Day 15, whether conducted in the hospital or contacted via phone or other digital media.

Safety/ Tolerability
	
Safety/Tolerability
 
Adverse events will be collected from the time of informed consent through Day 15. After Day 15, collect/record only Serious Adverse Events (SAEs) or those judged by the Investigator or designated person to be related to study drug, including but not limited to potential hematologic toxicities. Post-randomization adverse events will be those with an onset after the date and time of randomization.

Statistical Analysis
	
A separate, detailed statistical analysis plan (SAP) will be finalized prior to locking the database. All analyses of safety and efficacy for this study will be descriptive in nature and presented by group. Subject demographics and baseline characteristics will be summarized. Subject data listings will also be provided.
 
Summaries for quantitative variables will include the mean, median, quartiles, standard error, minimum, and maximum. For qualitative variables, the summaries will include the number and percentage of subjects for each outcome, and the 95% CI, when appropriate. Any statistical testing will be considered exploratory and descriptive. All computations will be performed using SAS® (Version 9.4 or higher). Safety and tolerability will be assessed in terms of AEs, SAEs, safety laboratory data, and NEWS2 Assessments.
 
Adverse event data will be descriptively evaluated. All AEs will be reported in data listings. The incidence of post randomization adverse events, defined as AEs occurring after randomization will be tabulated by Medical Dictionary for Regulatory Activities (MedDRA) preferred term and system organ class, and by severity and relationship to study treatment. All laboratory results, NEWS2 Criteria, and other clinical measures will be summarized using appropriate descriptive statistics.

PROTOCOL NUMBER: CCB-CRISIS-01  
PROTOCOL VERSION DATE: 01MAY2020

Page 15 of 55

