## **6 TRIAL ENDPOINTS**

### **6.1 Primary Endpoint**

- Safety/tolerability measured by rates of post randomization adverse events and hematology/chemistry safety labs.

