### Days 1 - 7 (8 AM ± 8 hours)

- If Day 1 is different date from Screening, confirm subject continues to meet all inclusion and no exclusion criteria.
- Randomize the subject (record date and time of randomization).
- Review Progress Notes and medication records to collect any new or changes to ongoing adverse events or new or changed concomitant medications since previous visit (may be omitted on Day 1 if Screening visit was conducted on same day as Study Day 1). Repeat on Day 7.
- Collect SOC hematology/chemistry results from the EHR on Day 1 (pre-dose) and Day 7 (may be omitted for Day 1 if Screening visit conducted on same date as Study Day 1). Ensure that Day 1 samples are obtained prior to first dose of study drug, if applicable.
- Days 1 (pre-dose), 3, 5, 7:
  - Collect NEWS2 Assessments from the EHR.
  - Collect results for inflammatory markers from EHR for those analyzed locally; collect, process and ship samples for DHO/brequinar PK and cytokine panel to be analyzed at the central laboratory per the Laboratory Manual.
  - Collect and process SARS-CoV-2 nasopharyngeal viral load samples.
  - Record hospitalization status (hospitalized, hospitalized in ICU, discharged) (Day 1 already recorded as part of Inclusion criteria, do not record again).
- Dispense study medication (Days 1 through 5 if in brequinar group) and record date and time of brequinar administration. Keep the drug administration interval as close as possible to 24h. Ensure Day 1 labs are drawn prior to first brequinar dose on Day 1. If a subject taking brequinar is discharged prior to Day 5, administer final dose on day of discharge. Do not give subject study drug to take home.

PROTOCOL NUMBER: CCB-CRISIS-01  
PROTOCOL VERSION DATE: 01MAY2020

Page 34 of 55

- Drug accountability Day 7  $\pm$  2 days.

**Final Visit Day 15** (8 AM  $\pm$  2 days) or Hospital Discharge Day if earlier than Day 15

- Review Progress Notes and the medication record to collect information for any adverse events or new concomitant medications since Day 7 (from EHR if subject still hospitalized, otherwise by phone or other digital media).
- Collect results for SOC hematology/chemistry from the EHR if subject still hospitalized.
- Collect inflammatory markers from EHR for those analyzed locally; collect samples for DHO and cytokine panel to be analyzed at the central laboratory if subject still hospitalized.
- Collect NEWS2 Assessments from the EHR.
- Collect nasopharyngeal viral load sample.

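### Two AE recording rules are tied to dosing and study drug, which the SOC-alone arm does not have, so worsening and late non-serious AEs may be recorded differently by arm

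*Protocol*

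**What the plan says.** All references are to the 01MAY2020 version unless stated.

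- **Endpoint.** Section 6.1: "Safety/tolerability measured by rates of post randomization adverse events and hematology/chemistry safety labs". Section 11 presents all analyses by group, and Section 11.2 tabulates post-randomization AEs. The Synopsis (Safety/Tolerability) sets the start of the window: "Post-randomization adverse events will be those with an onset after the date and time of randomization". None of these places gives an end.
- **Worsening.** Section 10: "For any pre-existing condition or abnormal laboratory finding that changes in severity after dosing, this change should be recorded as an AE".
- **General collection.** Section 10: "All adverse events will be collected from the time of informed consent through Day 15".
- **After Day 15.** Section 10: "After Day 15, collect/record only Serious Adverse Events (SAEs) or those judged by the Investigator or designated person to be related to study drug".
- **Laboratory values.** Section 10 judges these from enrollment: "Abnormal laboratory values or test results occurring after study enrollment constitute AEs only if" they cause signs or symptoms, are clinically significant or need therapy.
- **Late SAEs.** Section 10 says that SAEs "experienced after 30 days post the last dose of study drug should only be reported to the sponsor" if the investigator suspects that the study drug caused them.
- **Day 1 and Day 7 review.** Section 9.5: "Review Progress Notes and medication records to collect any new or changes to ongoing adverse events".
- **Arms.** Section 7.1 plans about 8 subjects on SOC alone and about 16 on SOC plus brequinar. Section 8.7.3 makes assignment open label.

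**The concern.** The primary comparison is between a dosed arm and an arm with no study drug. A rule that decides whether an event becomes an AE should therefore start at a moment that exists in both arms. Two rules in Section 10 do not: the worsening rule starts at dosing, and the rule for non-serious events after Day 15 depends on relatedness to study drug.

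Worsening of something already present is a likely route to an AE here. Every subject has COVID-19, and inclusion criterion 2 in Section 7.2 requires at least one listed risk factor: a chronic disease such as hypertension, diabetes, or kidney, lung or heart disease, or age over 65, or BMI above 30. If site staff, who know the assignment, apply the dosing wording literally, a worsening could be recorded on brequinar and passed over on SOC. Part of any AE excess on brequinar would then come from the recording rule and not from the drug.

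**Working it through.** The protocol gives no AE rate, effect size or power to reproduce, so the check is mainly a reading of the rules by arm.

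**1. Worsening of a condition present at baseline.** Section 10 sends conditions present before consent to medical history. The sentence anchored to dosing is the only one in Section 10 that expressly turns a worsening of such a condition into an AE. The Section 9.5 review asks for changes to ongoing AEs, and a condition held as medical history is not an ongoing AE. For laboratory findings, the enrollment-based rule does reach SOC, but it carries a clinical-significance condition that the worsening sentence does not state.
- Brequinar: an explicit instruction, starting at the first dose.
- SOC: no defined start; recording relies on the general rule that all AEs are collected through Day 15.

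**2. Non-serious AEs after Day 15.**
- Brequinar: recorded if judged related.
- SOC: in practice never, because there is no study drug to be related to.
- Since the tabulation has no stated end, late non-serious events can enter the table from one arm only.

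**3. SAEs after Day 15.** Collected in both arms. The later limit runs from the last dose. With a last dose on Day 5, it falls on study Day 5 + 30 = 35. For SOC there is no last dose, so the limit is undefined. Read literally, it restricts reporting on brequinar and not on SOC, the opposite direction to items 1 and 2.

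**4. What one event is worth.** Arm sizes: 24 × 1/3 = 8 and 24 × 2/3 = 16, which agrees with Section 7.1.
- One SOC subject: 1/8 = 12.5 percentage points.
- One brequinar subject: 1/16 = 6.25 percentage points.
- The SOC figure is a maximum for the rate of subjects with any AE, since a subject who already has another recorded AE would not change that rate.

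**The case against.** The strongest reply is that the general rules already cover SOC. All AEs from consent through Day 15 are collected without limit by arm, as are SAEs afterwards. Laboratory values are judged from enrollment. Section 10.6 has clinically significant out-of-range results reported as AEs. The worsening sentence says what should be recorded and does not forbid recording anything else. This largely stands, and it rules out three stronger readings that a reader might infer.

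- **That worsening and late events are counted only on brequinar.** The documents do not say so. A careful site could record every SOC worsening under the general rules, and late SAEs are collected in both arms.
- **That the artificial difference can be computed.** Assume the same worsening probability w in both arms, from 0.10 to 0.40 (an assumption; the documents give no rate). If the dosing sentence were the only route, SOC would show 0 of 8 against 16 × w = 1.6 to 6.4 of 16, a spurious difference of 10 to 40 points. The chance of losing at least one SOC worsening, 1 − (1 − w)^8, would be 57% to 98%. The sentence is not the only route, so these are ceilings and not forecasts.
- **That the sections contradict each other on time zero.** Consent starts collection, and randomization defines the tabulated subset. The Synopsis states both together, and they serve different purposes.

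Other points limit the weight. All analyses are descriptive (Section 11), so no test or decision threshold depends on the difference. Few late non-serious AEs would be sought: Day 29 is a survival check in Section 9.5, and Appendix A shows no AE review there. This is not complete, since Section 10.6 adds a Day 29 contact for subjects discharged before Day 7 and says that phone visits ask about bleeding signs. The end of the AE table could be set in the SAP, which is not shown. What gets recorded, however, is fixed by the protocol and cannot be recovered at analysis.

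**Conclusion.** The point holds as an ambiguity that depends on arm, in rules that feed the primary endpoint. It is not a stated exclusion of SOC subjects. The worsening rule and the 30-day SAE limit have no defined start on SOC, and non-serious AEs after Day 15 can in practice be recorded only on brequinar. Open-label assignment makes different application by arm possible.

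The size cannot be estimated from the documents. The only firm figure is the sensitivity: one unrecorded SOC event moves that arm's rate by up to 12.5 points. The net direction is not certain either, because the 30-day limit works against the other two rules.

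The change should be made, because it is cheap and removes an arm-dependent recording rule from the primary comparison. The conclusion is limited to the 01MAY2020 text. Later versions, through 10 September 2020, are listed, but their Section 10 is not in the part at hand, so whether the wording persists cannot be checked.

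**What to change.** 1. In Section 10, replace the severity change after dosing with 'worsens after randomization', and say that this applies to both arms and to conditions held as medical history.
2. Limit the between-arm AE comparison to onset from randomization through Day 15. List drug-related AEs with later onset separately for the brequinar arm.
3. Define the 30-day SAE reporting window by study day, the same in both arms, so that it has a meaning for SOC subjects.
4. Confirm whether later protocol versions already carry these changes.

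The cost is a few words in Section 10 and one line in the analysis plan. No new visits, samples or data are needed.
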